**Table 5-2. Monthly Intervals for Sleep Associated Endpoints**

Study Period	Assessment Timepoint	Monthly Interval	
		Start Date/Time a	End Date/Time b
Baseline Period	Baseline	Max (Earliest recorded sleep start date, week -4 visit date)	Day 1 dose date/time
Double-blind Treatment Period	Week 4 (Month 1)	Day 1 dose date/time	Week 4 dose date/time
	Week 8 (Month 2)	Week 4 dose date/time	Week 8 dose date/time
	Week 12 (Month 3)	Week 8 dose date/time	Week 12 dose date/time
	Week 16 (Month 4)	Week 12 dose date/time	Week 16 dose date/time
	Week 20 (Month 5)	Week 16 dose date/time	Week 20 dose date/time
	Week 24 (Month 6)	Week 20 dose date/time	≤ Week 24 visit date

a Start Date/Time = End date/time of previous monthly interval if IP dose date is not available

b End Date/Time = Start date/time of current monthly interval + 27 if IP dose date is not available

### 5.4.2 Analysis Visits for Endpoints Based on Monthly Collection

Since the actual visit for a subject may not exactly coincide with their targeted visit date, the actual visit date is mapped to the analysis visit as in [Table 5-3](#), [Table 5-4](#), and [Table 5-5](#). Any data occurred after EOS date will not be included in the analysis.

For by-visit summaries, if more than one visit with non-missing measurement (including the unscheduled visits, ie, CPEVENT = 'UNSCHED') fall within the same visit window, the following rules will be applied according to the order described below for selecting one visit per visit window for summary:

1. Scheduled visit will be used regardless of the distance from the target day. Unscheduled visit will only be used when there is no measurement from scheduled visit in the visit window.
2. The visit closest to the target day among visits of the same type (all scheduled visits or all unscheduled visits) will be considered for analysis.
3. If two assessment dates are equidistant from the target date, the latter visit will be considered for analysis.

**Table 5-3. Modified MIDAS and MFIQ Analysis Visit Windows**

Study Period	Analysis Visit	Target Day	Visit Window (Study Day)
Double-blind Treatment Period	Day 1 (Baseline)	1	Last measurement ≤ Day 1
	Week 4 (Month 1)	29	16 to 43
	Week 8 (Month 2)	57	44 to 71
	Week 12 (Month 3)	85	72 to 99
	Week 16 (Month 4)	113	100 to 127
	Week 20 (Month 5)	141	128 to 155
	Week 24 (Month 6)	169	156 to 183

**Table 5-4. PHQ-9, GAD-7, PSQI, ESS, Patient Satisfaction at Work and PVT Analysis Visit Windows**

Study Period	Analysis Visit	Target Day	Visit Window (Study Day)
Double-blind Treatment Period	Day 1 (Baseline)	1	Last measurement ≤ Day 1
	Week 4 (Month 1)	29	16 to 43
	Week 12 (Month 3)	85	72 to 99
	Week 24 (Month 6)	169	156 to 183

**Table 5-5. HRU Analysis Visit Windows**

Study Period	Analysis Visit	Target Day	Visit Window (Study Day)
Double-blind Treatment Period	Day 1 (Baseline)	1	Last measurement ≤ Day 1
	Week 24 (Month 6)	169	156 to 183

## 5.5 Subject Disposition

### Randomized

Individuals are considered randomized if they have been assigned a randomization number. Randomized individuals are referred to as “subjects”.

### Exposed to Investigational Product

Subjects are defined as exposed if they receive at least one dose of investigational product.

### Completing Investigational Product

Subjects are defined as completing investigational product if the primary reason for ending IP on End of IP eCRF is “Completed”.

### Completing Study

Subjects are defined as completing study if they complete the entire 24 weeks of study evaluation. It will be derived from the End of Study eCRF with “Completed” as the primary reason for ending study.

### On-study

Subjects are considered on-study if they have been randomized and have not yet had their EOS visit.

## 5.6 Arithmetic Calculations

### Duration of Migraine

The number of years from the diagnosis date (DXDT) of migraine (migraine with aura or migraine without aura, whichever is earlier) to the date informed consent is signed.

Observed Portion	Missing Portion	Duration of Migraine (Years)
Year, Month, Day	NA	(Informed Consent Date – DXDT) / 365.25
Year, Month	Day	[Year(Informed Consent Date) – Year(DXDT)] + [Month(Informed Consent Date) – Month(DXDT)] / 12 a
Year	Month, Day	[Year(Informed Consent Date) – Year(DXDT)] a

a If it equals 0, add 1/12 years (ie, 1 month) to avoid a disease duration of 0.

### **Duration of IP Exposure**

Minimum (Last Dose Date + 27, EOS Date) – First Dose Date + 1

### **Change From Baseline**

Postbaseline monthly value – Baseline, as defined in Section 5.4.

If the baseline or postbaseline value is missing, the change from baseline value will be set to missing.

### **Mean Monthly Change From Baseline Over Multiple Months**

Mean monthly change from baseline is the arithmetic mean of the monthly change from baseline values for the months considered with observed data, if there is at least one observed monthly value.

### **Sum of Monthly Changes From Baseline Over the 6-month DBTP**

Sum of monthly changes from baseline over the 6-month DBTP is calculated as the arithmetic mean of the monthly change from baseline over the same 6-month period times 6.

Note: This prorated value will be used to provide summary statistics of the primary efficacy endpoint.

### **Subject Incidence**

The subject incidence for a given event in a given period is defined as the number of subjects with at least one reported occurrence of the event divided by the number of subjects who enter that period (ie, number of at-risk subjects). For subjects with multiple occurrences of the same event in a given period, the event will only be counted once per subject in that period.

## **5.7 Disease Characteristics**

### **Treatment Failure of Prior Migraine Preventive Medications**

Treatment failure of prior migraine preventive medications is determined by “Reason for Stopping” as “Lack of efficacy” or “Adverse reaction” or “Intolerance” on the Prior Migraine Prophylactic Medication eCRF.

## **6. Analysis Sets**

### **6.1 Full Analysis Set**

The respective full analysis set (FAS) consists of all subjects who were randomized in the study through traditional study sites or DCTS. Analysis of disposition, demographic

and baseline characteristics, and important protocol deviations will utilize the respective FAS.

## **6.2 Efficacy Analysis Set**

The respective efficacy analysis set (EAS) consists of a subset of subjects from traditional study sites or DCTS who receive at least 1 dose of IP and have a baseline value and at least 1 post baseline value for the endpoint of interest. Subjects will be analyzed according to their randomized treatment, regardless of the treatment received. Primary analysis of the efficacy endpoints will utilize the respective EAS.

## **6.3 Safety Analysis Set**

The respective safety analysis set (SAS) will consist of all randomized subjects from traditional study sites or DCTS who received at least 1 dose of IP. Subjects will be analyzed according to the randomized treatment unless a subject has received the incorrect randomized treatment during the entire DBTP. Analysis for safety endpoints and summary of IP administration will utilize the respective SAS.

## **7. Planned Analyses**

The primary analysis (or final analysis since there is only one milestone analysis for this study) will occur after all subjects have completed their week 24 visit (or discontinued from the study). The DBTP treatment assignment will be unblinded and all efficacy and safety analyses will be conducted and reported by the DBTP treatment group. The primary analysis at the end of the study will be based on cleaned, locked data.

## **8. Data Screening and Acceptance**

### **8.1 General Principles**

The objective of the data screening is to assess the quantity, quality, and statistical characteristics of the data relative to the requirements of the planned analyses.

### **8.2 Data Handling and Electronic Transfer of Data**

The Amgen Global Study Operations-Data Management (GSO-DM) department will provide all data to be used in the planned analyses. This study will use the RAVE database. The database will be subjected to edit check outlined in the Data Management Plan (DMP). eDiary data, physical activity and sleep data collected through wearable, pharmacogenetic, and biomarkers data is outside of RAVE database. All the datasets to be used for planned analyses will be received from GSO-DM department. Additional details will be provided in the DMP and Data Transfer Plan (DTP).

### 8.3 Handling of Missing and Incomplete Data

Subjects may miss specific data points for a variety of causes. In general, data could be missing due to a subject's early withdrawal from study, a missed visit, or inability to evaluate an endpoint at a point in time. For this study, most of the efficacy endpoint will be collected via eDiary and subjects could miss entering several days of data in each monthly interval. The general procedures outlined below describe what will be done when a data point is missing.

Missing daily data in the calculation of monthly measurements about subjects' migraine and non-migraine headaches will be handled using the following proration method, also described in Section 5.1.1.

- For each monthly interval with  $\geq 14$  days of eDiary use:
  - Monthly frequency measurements will be prorated to 28-day equivalents. Prorated result does not need to be rounded.
  - Monthly average scores will be calculated as the average of observed scores.
- For monthly intervals with  $< 14$  days of eDiary use, all monthly measurements will be set as missing.

Missing monthly efficacy measurements will not be imputed in the primary analysis method utilizing a generalized linear mixed model to handle missing data under MAR assumption. In the sensitivity analysis on primary and secondary efficacy endpoints, missing data in monthly values will be handled using multiple imputation (MI) with assumption of missing not at random (MNAR) (with control-based pattern imputation).

For the descriptive summary the mean monthly value over months 4, 5, and 6 is calculated using the arithmetic mean of observed monthly values from each of months 4, 5, and 6 of the DBTP. Therefore, a subject with at least one monthly value at months 4, 5, and 6 will contribute to the summary statistics.

For the descriptive summary the primary endpoint, sum of monthly changes from baseline in MIDAS total score over the 6-month DBTP, will be prorated as follows for subjects with missing data in monthly changes from baseline:

$$\frac{\text{Sum of observed monthly changes from baseline in MIDAS score within 6 month DBTP}}{\text{Number of months with observed monthly values within 6 month DBTP}} \times 6$$

Missing safety endpoints will not be imputed. Missing or incomplete dates will be listed as reported, except for incomplete start date of an adverse event or concomitant medication, which will be imputed as follows:

Missing	Imputation	Exception on adverse event start date
Day	01	Default to study day 1 if an adverse event started the same year and month as study day 1 and the flag indicates that the adverse event started on or after the first dose of investigational product on the Events eCRF
Day/Month	01 JAN	Default to study day 1 if an adverse event started the same year as study day 1 and the flag indicates that the adverse event started on or after the first dose of investigational product on the Events eCRF
Day/Month/Year	None	-

#### 8.4 Detection of Bias

This study has been designed to minimize potential bias by allocating treatment groups randomly, assessing endpoints and handling withdrawals without knowledge of the treatment. Other factors that may bias the results of the study include:

- important protocol deviations likely to impact the analysis and interpretation of the efficacy endpoints
- inadvertent breaking of the blind before formal unblinding
- investigational product dosing non-compliance
- the timing of and reasons for early withdrawal from treatment and from study

The incidence of these factors may be assessed. Important protocol deviations will be listed and/or tabulated. If necessary, the incidence of other factors will be tabulated.

Any breaking of the blind for individual subjects prior to formal unblinding of the study will be documented in the CSR.

The reasons for early withdrawal from treatment and from study will be tabulated and/or listed.

#### 8.5 Outliers

Histograms will be examined to identify outliers in any of the continuous variables used in the analyses. Unexpected and/or unexplained values in categorical data will be identified by utilizing frequency tables.

Outliers due to data entry errors will be corrected by the study team before final database lock. The validity of any questionable values or outliers will be confirmed. Outliers or any questionable values with confirmed validity will be included in the analyses. However, ad-hoc sensitivity analyses may be conducted to evaluate the influence of extreme values in the data.

## 8.6 Distributional Characteristics

Continuous endpoints of change from baseline value will be analyzed under normality assumption. If they deviate appreciably from normality, appropriate transformations or the non-parametric alternatives will be used, such as Quade test (Quade D, 1966) may additionally be considered.

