### 10.4.2.2 Efficacy Analyses

Endpoint	Statistical Analysis Methods
Primary	
Under the assumption of missing at random (MAR), the primary endpoint will be analyzed using a linear mixed effects model including treatment group, baseline value, scheduled visit, and the interaction of treatment group with scheduled visit, without any imputation for missing data.
 
Multiple imputation (MI) with the assumption of missing not at random (MNAR) will be used as a sensitivity analysis to handle missing data at each assessment time point, using the analysis of covariance (ANCOVA) model including treatment group and baseline value.

Secondary	
Under the assumption of MAR, the secondary endpoints will be analyzed using a linear mixed effects model including treatment group, baseline value, scheduled visit, and the interaction of treatment group with scheduled visit, without any imputation for missing data.
 
MI with the assumption of MNAR will be used as a sensitivity analysis to handle missing data at each assessment time point, using the ANCOVA model including treatment group and baseline value.

Exploratory	
Detailed primary analysis method for exploratory endpoints will be described in the SAP. No sensitivity analysis will be performed for exploratory endpoints.

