##### **4.2 Subgroups**

The primary and secondary endpoints will be summarized in the subgroups defined by number of prior treatment failures (1, 2, and 3 or more treatment failures) for the traditional sites only.

The subgroups will be re-examined for appropriateness and may be re-categorized (due to small sample size, for example, if there are < 10% of subjects within a subgroup) before unblinding.

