## 9. Statistical Methods of Analysis

### 9.1 General Considerations

All analyses will be conducted separately for subjects enrolled from traditional sites and subjects from DCTS. Formal statistical hypothesis testing for the primary and secondary endpoints will be performed for subjects enrolled from traditional sites only. Subject characteristics for both traditional sites and DCTS will be summarized descriptively.

Summary statistics by each treatment group will be tabulated at each assessment time point if applicable. For continuous endpoints, the descriptive statistics include: number of observations, means, medians, standard deviations, standard errors, first and third quartiles, minimums and maximums, and 2-sided 95% CIs of the means (CIs will be provided for efficacy endpoints only). For categorical endpoints, the summaries will contain the number and percentage of subjects in each category.

The primary analysis method utilizing a repeated measures linear mixed effects model will include all observed data regardless of treatment adherence.

A sequential testing procedure will be used to maintain the family-wise type 1 error  $\alpha = 0.05$  between the primary and secondary endpoints following the order of modified MIDAS total score, MMD, WPAI, MFIQ physical function, MFIQ usual activity, and MFIQ social function endpoints. An endpoint will only be tested if the endpoint tested in the previous step is statistically significant at 2-sided significance level of 0.05.

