**Table 9-1. Primary Efficacy Endpoint Summary Table**

Endpoint	Primary Summary and Analysis Method	Sensitivity Analysis
Sum of monthly changes from baseline in modified MIDAS total score over the 6-month double-blind treatment period (DBTP)  (Note: Results from individual time point during the DBTP will also be generated in the same generalized linear mixed effect model.)	

1. Summary statistics by visit using observed data at each visit and the calculated sum of each monthly change from baseline value over 6 months

2. Least squares means from a generalized linear mixed effect model including treatment group, scheduled visit, interaction of treatment and scheduled visit and baseline value using observed data

3. Test treatment difference (AMG 334 – Placebo) using a contrast from the model in #2.

	MI with assumption of MNAR (control-based pattern imputation)

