### 9.5.1 Analyses of Primary and Secondary Efficacy Endpoints

The primary analysis of the primary and secondary endpoints will be performed using a generalized linear mixed model based on observed monthly data with appropriate contrasts for treatment comparison relative to placebo for the corresponding efficacy endpoints: sum of monthly changes from baseline value over the 6-month DBTP, and change from baseline in mean monthly values or mean domain scores over months 4, 5 and 6. The model will include treatment, scheduled visit, treatment-by-visit interaction, and baseline value as covariates. If applicable, the first-order autoregressive covariance structure is assumed. Least squares means (LSMs) for each treatment group, standard errors, associated 95% confidence intervals, difference of LSMs compared to placebo group, associated 95% confidence intervals and nominal two-sided p-values will be tabulated by visit, as well as for the mean monthly values over months 4, 5, and 6 of the DBTP.

Sensitivity analysis described below will be performed for the primary and secondary endpoints:

1. MI with assumption of MNAR (control-based pattern imputation).
2. Primary summary and analysis by the subgroup of treatment failure of prior migraine prophylactic medications (Section 4.2)

The purpose of the subgroup analyses is to explore if the treatment effect varies across subgroups of interest. Analysis within each interested subgroup will be performed using the same primary analysis method for the same endpoint. The treatment difference with associated 95% confidence interval and p-value will be reported within each subgroup.

The heterogeneity of the treatment effect across the subgroups will be evaluated by examining the treatment-by-subgroup interaction p-value obtained from the primary analysis model with the addition of treatment-by-subgroup interaction.

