## **10. Changes From Protocol-specified Analyses**

In addition to modified MIDAS total score, absenteeism score and presenteeism score will also be analyzed as exploratory endpoints.

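### Could SAP 8.6's wording on non-normal data let a transformed or Quade analysis displace the mixed-model contrast as the confirmatory test?

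*SAP*

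**What the plan says.** SAP 8.6 belongs to Section 8, on data screening and acceptance. It assumes normality for continuous change-from-baseline endpoints and then says that, on an appreciable departure, "appropriate transformations or the non-parametric alternatives will be used, such as Quade test (Quade D, 1966) may additionally be considered". It does not define an appreciable departure, name a transformation, choose between a transformation and a rank test, or say when the decision is taken.

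The methods are in Section 9. SAP 9.5.1 states: "The primary analysis of the primary and secondary endpoints will be performed using a generalized linear mixed model based on observed monthly data". Tables 9-1 and 9-2 give the test for the primary and secondary endpoints in the same words: "Test treatment difference (AMG 334 – Placebo) using a contrast from the model in #2". Protocol 10.4.2.2 agrees: "the primary endpoint will be analyzed using a linear mixed effects model including treatment group, baseline value, scheduled visit". The only entry in the tables' sensitivity column is control-based multiple imputation; 9.5.1 adds a subgroup analysis.

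SAP 9.1 sets the fixed sequence at two-sided 0.05: "An endpoint will only be tested if the endpoint tested in the previous step is statistically significant". SAP Section 10, which lists departures from the protocol, has one entry: "In addition to modified MIDAS total score, absenteeism score and presenteeism score will also be analyzed as exploratory endpoints".

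**The concern.** A mandatory phrase and an optional one stand in the same sentence, and they assign different roles. If the mandatory phrase governs, a finding of non-normality would replace the mixed-model contrast with something else. That would matter in two ways. A Quade test or a log-scale analysis does not estimate the difference in means, which SAP 2.1 declares as the summary measure of the primary estimand. Its p-value would also open or close the sequence in 9.1.

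The trigger is not far-fetched. The modified MIDAS total runs from 0 to 93, and entry requires a day 1 score above 3, so skewed scores are plausible.

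Other sections of the SAP set limits that 8.6 lacks. SAP 8.5 gives its extra work a status: "ad-hoc sensitivity analyses may be conducted to evaluate the influence of extreme values in the data". SAP 4.2 gives regrouping of subgroups a time limit: "if there are < 10% of subjects within a subgroup) before unblinding". If the analyst could choose the test after seeing results, type I error would exceed 5%.

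**Working it through.** **1. The passages side by side.**

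| Place | Role given to the mixed model | Mention of a transformation or rank test |
|---|---|---|
| Protocol 10.4.2.1, 10.4.2.2 | Primary analysis | None |
| SAP 9.1, 9.5 | Primary analysis | None |
| SAP 9.5.1, Tables 9-1 and 9-2 | Primary analysis, tested by contrast | None |
| SAP 10 | No change of test declared | None |
| SAP 8.6 | Not mentioned | Yes, with both phrases |

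Replacing the test would be a departure from the protocol, and Section 10 would have to declare it. It does not. The word additionally in 8.6 also makes sense only if the main analysis stays in place.

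**2. The plan's own figure.** Inputs from SAP Table 3-1: 120 per arm, difference -20, SD 43, two-sided 0.05.
- SE = 43 × √(2/120) = 5.551.
- 20/5.551 = 3.603, and Φ(3.603 − 1.960) = Φ(1.643) = 0.950. The noncentral t with 238 df gives 0.948.
- The stated 94% is reproduced to within rounding. Nothing in 8.6 bears on it.

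**3. Does the planned test fail under skewness?** Simulation on assumed data, 4,000 trials per case:
- 120 per arm; gamma-type scores kept within 0 to 93, baseline above 3.
- SD of the six-month sum about 43; monthly correlation 0.3, 0.6 or 0.8; residual skewness 1.1 to 1.2.
- 12% dropout unrelated to arm.

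Rejection with no effect (Monte Carlo SE 0.34 points):
- Mixed-model contrast: 4.8% to 4.9%.
- Quade on the prorated sum: 5.0% to 5.2%.
- Mixed model on logged scores: 4.5% to 5.2%.

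Each test, fixed in advance, holds its level.

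**4. The literal reading: switch tests on the distribution.** Simulation with no effect, 120 per arm, one visit, lognormal data with log-scale SD 0.3, 0.7 and 1.0, 10,000 runs each. A Shapiro-Wilk test on the residuals selects ANCOVA or Quade. Rejection was 4.9%, 5.2% and 4.6% (Monte Carlo SE √(0.05 × 0.95/10,000) = 0.22 points). The gate chose Quade in 98% to 100% of runs, so this mainly shows that Quade holds its level. A similar gate with ANCOVA on the six-month sum gave 4.3% to 5.0%.

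**5. Picking the smallest p-value.** In the setting of step 3, taking the better of mixed model and Quade after seeing both rejects 6.7% to 7.3% of null trials. Adding the log analysis gives 8.1% to 9.0%. SAP 8.6 authorises neither, because its condition concerns the distribution and not the result. These rates are also not a ceiling, since no list of transformations is given.

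**6. How often would the choice change the verdict?** Treat the two test statistics as bivariate normal with equal means and correlation 0.88 to 0.92. With no effect they disagree in 4.4% to 3.7% of trials, in line with the simulated 3.5% to 4.5%. At the planned effect (mean 3.603) they disagree in 4.0% to 3.3%, about 1 trial in 25 to 30. At half that effect, 10/5.551 = 1.801, power is Φ(1.801 − 1.960) = 44% and disagreement is 15.6% to 12.7%. So it does matter which test counts, but the plan already says which one that is.

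**The case for a change.** The strongest case for acting is that no sentence makes 8.6 subordinate to Section 9. The SAP limits similar discretion in 4.2 and 8.5, so its silence in 8.6 stands out. Even as a supplement, a Quade analysis has no defined place: it is not among the listed sensitivity analyses, and its input per subject is not stated. The repair would be one line and would leave the data, sample size and confirmatory test as they are.

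All of that is true of the wording. What does not stand is the step from loose wording to a threatened result. The confirmatory test is named repeatedly in the sections that govern testing, and one unclear sentence in the data-screening section does not override them. The inflated error rates need selection on p-values, which the text does not permit. The repair would keep the same test and write down the role that a careful reader already gives the alternatives.

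**Conclusion.** No change to the plan follows. SAP 8.6 is a drafting slip, probably two clauses run together, and it leaves out detail about an optional analysis. Following the plan still gives a mixed-model contrast tested at 5%, and that is the p-value that drives the sequence in 9.1. A transformed or Quade analysis, if run, is supportive.

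On size: the planned contrast rejected 4.8% to 4.9% of null trials under the skewed scores assumed here, and a distribution-based switch stayed between 4.3% and 5.2%. Rates of 6.7% to 9.0% arise only if the result decides the test. The score distributions, correlations and dropout are assumptions, since the documents give only the SD of 43, the score range and the entry threshold. The conclusion rests mainly on the text of Section 9 and Protocol 10.4.2.2. It would change only if a transformed or Quade result were reported as the confirmatory test.
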